 - e. Serum creatinine ≤1.5 mg/dL (≤133 µmol/L)
 - f. Aspartate aminotransferase (AST) and alanine aminotransferase (ALT) concentrations must be \leq 2 times the upper limit of the normal (ULN) range for the laboratory conducting the test
 - g. Total bilirubin $\leq 1.5 \times \text{ULN}$ (isolated bilirubin $\geq 1.5 \times \text{ULN}$ is allowed for those participants with known Gilbert's syndrome).

Sex and Contraceptive/Barrier Requirements

- 7. Male or female (according to their reproductive organs and functions assigned by chromosomal complement), to guide the criteria below.
- 8. A woman of childbearing potential must have a negative highly sensitive serum (beta human chorionic gonadotropin [B-hCG]) test result during screening and a negative urine pregnancy test at week 0, prior to randomization.

- 9. Before randomization, a woman must be
 - a. Not of childbearing potential
 - b. Of childbearing potential and
 - i. If heterosexually active, practicing a highly effective method of contraception (failure rate of <1% per year when used consistently and correctly) and agrees to remain on a highly effective method while receiving study intervention and until 12 weeks after last dose the end of relevant systemic exposure. The investigator should evaluate the potential for contraceptive method failure (eg, noncompliance, recently initiated) in relationship to the first dose of study intervention; however, the method selected must meet local/regional regulations/guidelines for highly effective contraception.

Note: If a participant's childbearing potential changes after start of the study (eg, a premenarchal woman experiences menarche) or the risk of pregnancy changes (eg, a woman who is not heterosexually active becomes active), a woman must begin using a highly effective method of contraception as described throughout the inclusion and exclusion criteria.

- 10. A woman must agree not to donate eggs (ova, oocytes) or freeze for future use for the purposes of assisted reproduction during the study and for a period of 12 weeks after the last administration of study intervention.
- 11. During the study and for at least 12 weeks after the last administration of study intervention, a male participant:

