Summaries of clinical laboratory tests by study intervention group over time will be provided for participants in the Safety Analysis Set:

- Summary of maximum NCI-CTCAE toxicity grade for post-baseline laboratory values through Week 48 and through Week 156.
- Shift tables for maximum NCI-CTCAE toxicity grade from baseline through Week 48 and through Week 156 will be summarized for the following lab parameters:
 - Hematology: hemoglobin, platelets, total WBC, absolute lymphocytes, and absolute neutrophils;
 - Chemistry: ALT, AST, alkaline phosphatase, and total bilirubin.
- Summary of maximum post-baseline measurement through Week 48 and through Week 156 for ALT, AST, alkaline phosphatase, and total bilirubin relative to ULN.

CONFIDENTIAL – FOIA Exemptions Apply in U.S.

- Summary of maximum post-baseline measurement through Week 48 and through Week 156 for ALT, AST, alkaline phosphatase, and total bilirubin relative to ULN among participants taking immunomodulators at baseline.
- Summary of maximum post-baseline elevated liver function tests through Week 48 and through Week 156 by the following categories for ALT, AST, alkaline phosphatase, and total bilirubin relative to ULN:
 - > 1 to \leq 3 x ULN
 - > 3 to \leq 5 x ULN
 - > 5 to \leq 10 x ULN
 - > 10 to \leq 20 x ULN
 - > 20 x ULN
- Summary of potential Hy's Law case (ALT or AST \ge 3 x ULN and total bilirubin \ge 2 x ULN or INR >1.5) through Week 48 and through Week 156.
- Box plots of observed laboratory values and change from baseline in laboratory parameters (hematology and chemistry) through Week 48 and through Week 156 will be provided.

Listings of participants with any abnormal post-baseline laboratory values of NCI-CTCAE grade ≥ 2 , participants with maximum post-baseline elevated liver function tests (AST or ALT >5xULN) and participants with potential Hy's Law case (ALT or AST $\geq 3 \times$ ULN and total bilirubin $\geq 2 \times$ ULN or INR >1.5), will also be provided by study intervention group, participant, and visit.

There will be no imputation for missing laboratory values.

Any laboratory values given as <X.X in the database will be imputed with the value of the number without the sign for the descriptive statistics and the calculation of changes from baseline, eg. a value of <2.2 will be imputed as 2.2 for the calculations.

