6.10. Appendix 10 Laboratory Toxicity Grading

The grading scale use for lab assessments is based on 'Common Terminology Criteria for Adverse Events (CTCAE) v5.0'.

If a laboratory value falls within the grading as specified below but also within the local laboratory normal limits, the value is considered to be normal and will be reset to grade 0.

Pre-baseline measurements will use the same grading ranges as applied to baseline measurements. In case a test has two sets of ranges – one for baseline normal and one for baseline abnormal, the one for baseline normal will be applied for all measurements taken pre-baseline and on baseline.

Text in gray italic in the table is present in the grading scale, but is not applied by Janssen when grading lab data.

CTCAE Term	Grade 1	Grade 2	Grade 3	Grade 4	Janssen implementation notes
Blood and lymphatic syst	em disorders	-			
Anemia	Hemoglobin (Hgb) <lln -="" 10.0="" dl;
<lln -="" 6.2="" l;
<lln -="" 100="" g="" l<="" td="">Hemoglobin (Hgb) <10.0 - 8.0 g/dL; <6.2 - 4.9 mmol/L; <100 - 80g/L	Hemoglobin (Hgb) <8.0 g/dL; <4.9 mmol/L; <80 g/L; transfusion indicated	Life-threatening consequences; urgent intervention indicated	Clinical signs and symptoms are not taken into consideration for grading.	</lln></lln></lln>	Hemoglobin (Hgb) <10.0 - 8.0 g/dL; <6.2 - 4.9 mmol/L; <100 - 80g/L	Hemoglobin (Hgb) <8.0 g/dL; <4.9 mmol/L; <80 g/L; transfusion indicated	Life-threatening consequences; urgent intervention indicated	Clinical signs and symptoms are not taken into consideration for grading.
Leukocytosis	-	-	>100,000/mm3; >100 x 10e9 /L	Clinical manifestations of leucostasis; urgent intervention indicated	Clinical signs and symptoms are not taken into consideration for grading; Added ranges in SI unit (x 10e9 /L)
Investigations					
Activated partial thromboplastin time prolonged	>ULN - 1.5 x ULN	>1.5 - 2.5 x ULN	>2.5 x ULN; bleeding	-	Clinical signs and symptoms are not taken into consideration for grading.

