Alanine aminotransferase increased	>ULN - 3.0 x ULN if baseline was normal; 1.5 - 3.0 x baseline if baseline was abnormal	>3.0 - 5.0 x ULN if baseline was normal; >3.0 - 5.0 x baseline if baseline was abnormal	>5.0 - 20.0 x ULN if baseline was normal; >5.0 - 20.0 x baseline if baseline was abnormal	>20.0 x ULN if baseline was normal; >20.0 x baseline if baseline was abnormal	Ranges defined for "abnormal baseline" are applied only if baseline > ULN. If baseline < LLN, then ranges for "normal baseline" are applied.
Alkaline phosphatase increased	>ULN - 2.5 x ULN if baseline was normal; 2.0 - 2.5 x baseline if baseline was abnormal	>2.5 - 5.0 x ULN if baseline was normal; >2.5 - 5.0 x baseline if baseline was abnormal	>5.0 - 20.0 x ULN if baseline was normal; >5.0 - 20.0 x baseline if baseline was abnormal	>20.0 x ULN if baseline was normal; >20.0 x baseline if baseline was abnormal	Ranges defined for "abnormal baseline" are applied only if baseline > ULN. If baseline < LLN, then ranges for "normal baseline" are applied.
Aspartate aminotransferase increased	>ULN - 3.0 x ULN if baseline was normal; 1.5 - 3.0 x baseline if baseline was abnormal	>3.0 - 5.0 x ULN if baseline was normal; >3.0 - 5.0 x baseline if baseline was abnormal	>5.0 - 20.0 x ULN if baseline was normal; >5.0 - 20.0 x baseline if baseline was abnormal	>20.0 x ULN if baseline was normal; >20.0 x baseline if baseline was abnormal	Ranges defined for "abnormal baseline" are applied only if baseline > ULN. If baseline < LLN, then ranges for "normal baseline" are applied.

CTCAE Term	Grade 1	Grade 2	Grade 3	Grade 4	Janssen implementation notes
Blood bilirubin increased	>ULN - 1.5 x ULN if baseline was normal; > 1.0 - 1.5 x baseline if baseline was abnormal	>1.5 - 3.0 x ULN if baseline was normal; >1.5 - 3.0 x baseline if baseline was abnormal	>3.0 - 10.0 x ULN if baseline was normal; >3.0 - 10.0 x baseline if baseline was abnormal	>10.0 x ULN if baseline was normal; >10.0 x baseline if baseline was abnormal	Ranges defined for "abnormal baseline" are applied only if baseline > ULN. If baseline < LLN, then ranges for "normal baseline" are applied.
CD4 lymphocytes	<lln -="" 500="" mm3;<="" td=""><500 - 200/mm3;	<200 - 50/mm3;	<50/mm3;		</lln>	<500 - 200/mm3;	<200 - 50/mm3;	<50/mm3;	

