* Grade 0 is assigned to a lab assessment when the lab test is described in the table, but the lab value is not assigned a grade 1 or higher.

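### For participants whose baseline liver test is above ULN, the shift tables grade baseline against ULN and later values against baseline, so a stable raised value reads as recovery and some real rises are hidden.

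*SAP*

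**What the plan says.** SAP Appendix 10 (6.10) defines CTCAE v5.0 grades. For ALT, AST, ALP, GGT and bilirubin each grade has two ranges. Grade 1 for ALT and AST, for example, is ">ULN - 3.0 x ULN if baseline was normal; 1.5 - 3.0 x baseline if baseline was abnormal". The implementation notes restrict the second range to participants whose baseline exceeds ULN. For a test with two range sets, the appendix adds that "the one for baseline normal will be applied for all measurements taken pre-baseline and on baseline". The baseline-relative set can therefore reach post-baseline values only. The footnote deals with values below the first range: "Grade 0 is assigned to a lab assessment when the lab test is described in the table" and no higher grade applies.

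SAP 5.7.3.1 plans "Shift tables for maximum NCI-CTCAE toxicity grade from baseline through Week 48 and through Week 156", covering ALT, AST, ALP and total bilirubin among the chemistry tests. No rule there puts the two grades on a common reference.

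Protocol 5.1, criterion 6, admits participants with raised values. ALT and AST may be up to "2 times the upper limit of the normal (ULN) range" and total bilirubin up to 1.5 x ULN, or higher if isolated in known Gilbert's syndrome. The criterion sets no limit for ALP.

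**The concern.** A shift table is read by comparing its row and column for the same participant. That comparison means something only if both grades come from one scale. Here, a participant who starts above ULN enters with a grade in multiples of ULN and leaves with a grade in multiples of baseline. On the second scale the entry point to grade 1 is "1.5 - 3.0 x baseline if baseline was abnormal" for ALT and AST, so a value that has not moved has no grade at all. The table then records an improvement that did not happen, and can record no change, or an improvement, where the test has risen.

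The stake is the reading of liver safety. Protocol 2.3.1 lists liver injury among the risks and describes transaminase increases as an identified adverse reaction of guselkumab.

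**Working it through.** The documents give no worked grade to reproduce, so the check applies the written rules to example values.

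**Inputs (SAP Appendix 10), lower grades only:**
- ALT and AST: grade 1 is >1 to 3.0 x ULN, or 1.5 to 3.0 x baseline; grade 2 is >3.0 to 5.0 x either reference; grade 3 is ">5.0 - 20.0 x ULN if baseline was normal; >5.0 - 20.0 x baseline if baseline was abnormal".
- ALP: grade 1 is >1 to 2.5 x ULN, or 2.0 to 2.5 x baseline; grade 2 is >2.5 to 5.0 x either reference.
- Bilirubin: grade 1 is >1 to 1.5 x ULN, or >1.0 to 1.5 x baseline; grade 2 is >1.5 to 3.0 x either reference.

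**Rule:** grade the baseline value on x ULN. If baseline > ULN, compute r = later value / baseline and grade r on the x baseline ranges; below the grade 1 range, assign 0.

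| Test | Baseline (x ULN) | Later (x ULN) | r | Shift as planned | Shift with x ULN at both times |
|---|---|---|---|---|---|
| ALT/AST | 2.0 | 2.0 | 1.00 | 1→0 | 1→1 |
| ALT/AST | 2.0 | 5.8 | 2.90 | 1→1 | 1→3 |
| ALT/AST | 1.9 | 5.8 | 3.05 | 1→2 | 1→3 |
| ALT/AST | 1.5 | 5.8 | 3.87 | 1→2 | 1→3 |
| ALP | 2.0 | 2.0 | 1.00 | 1→0 | 1→1 |
| ALP | 2.0 | 3.8 | 1.90 | 1→0 | 1→2 |
| Bilirubin | 1.5 | 1.5 | 1.00 | 1→0 | 1→1 |
| Bilirubin | 1.5 | 2.0 | 1.33 | 1→1 | 1→2 |
| Bilirubin (Gilbert's) | 2.0 | 2.0 | 1.00 | 2→0 | 2→2 |

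**Limits of the effect:**
- The table uses the maximum post-baseline grade. A false recovery therefore needs every post-baseline value to stay below the grade 1 threshold: under 1.5 x baseline for ALT and AST, under 2.0 x baseline for ALP, and at or below baseline for bilirubin.
- With baseline ALT 2.0 x ULN, the false-recovery zone runs to just under 1.5 × 2.0 = 3.0 x ULN, and nothing up to 3.0 × 2.0 = 6.0 x ULN appears as worsening.
- For 5.8 x ULN to appear as no shift, baseline must be at least 5.8 / 3.0 = 1.933 x ULN. With the eligibility cap of 2.0 x ULN, that is a narrow band. At 1.9 or 1.5 x ULN the table does show worsening, to grade 2 rather than 3.

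The example baselines of 2.0 x ULN are assumptions: for ALT and AST at the eligibility cap, for ALP where no cap is set, and for bilirubin in the Gilbert's exception.

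**The case against.** The strongest reply is that 5.7.3.1 does not depend on the shift tables to reveal liver injury. For the same four tests it plans the maximum post-baseline value relative to ULN, with counts in bands of >1 to 3, >3 to 5, >5 to 10, >10 to 20 and >20 x ULN. It also plans a summary and a listing of potential Hy's Law cases, box plots of change from baseline, and a listing of ALT or AST above 5 x ULN. The 5.8 x ULN participant is named in that last listing, and ALP of 3.8 x ULN falls in the >3 to 5 band. This stands. A reader might infer that worsening disappears from the safety report; it does not. The bands do not cross-tabulate baseline, however, so they do not make the shift tables right.

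A reader might also infer that the maximum-grade summary and the grade 2-or-higher listing are wrong, because they use the same grades. The documents do not support that. Both contain post-baseline values only, so there are no mismatched margins, and both follow the CTCAE v5.0 grading that SAP 5.7.3.1 and Appendix 10 specify; Protocol 9.4.5 also commits to the listing by CTCAE grade. Putting them on another scale would be a preference.

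Finally, SAP Section 1 states that the study was discontinued after four enrolments and that the planned analyses are kept for reference. This also stands, and it limits the practical consequence.

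**Conclusion.** The point holds for the shift tables of ALT, AST, ALP and total bilirubin, in participants whose baseline exceeds ULN. Their two margins are on different scales. An unchanged raised value is tabulated as recovery for all four tests (1→0, or 2→0 for bilirubin with baseline above 1.5 and up to 3.0 x ULN), subject to the maximum-grade condition shown above. Some real rises are hidden or understated. GGT has two range sets but is not in the shift tables.

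The size cannot be put as a count of wrong shifts, because the documents do not say how many participants start above ULN. If 5% to 20% did, the planned 185 per arm would give 0.05 × 185 = 9 to 0.20 × 185 = 37. A reader might take that as the number misclassified. It is an upper bound on an assumed prevalence: participants who return to normal are correctly grade 0, and some rises have the same grade on both scales.

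The rule is wrong as written, but its effect is limited to these tables, and with four participants enrolled it is minor in practice. It matters mainly if the text is reused.

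**What to change.** In SAP 5.7.3.1 and Appendix 10, state that for the shift tables only, baseline and post-baseline values of ALT, AST, ALP and total bilirubin are both graded on the x ULN (baseline-normal) ranges. Leave the maximum-grade summary and the grade 2-or-higher listing on the stated CTCAE v5.0 rule. Using the x baseline ranges at both times would also remove the false recovery (ALT 2.0 x ULN unchanged becomes 0→0, and a rise to 5.8 x ULN becomes 0→1). The x ULN choice is simpler because Appendix 10 already grades baseline that way.

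The cost is one extra derived grade variable and a footnote. For participants with a raised baseline, the shift-table grade can differ from the CTCAE grade in other tables. A participant with Gilbert's syndrome and stable bilirubin above 1.5 and up to 3.0 x ULN would be shown as grade 2 at both times, which is no shift. Participants with a normal baseline are unaffected.

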6.11. Appendix 11 Imputation Rule

• Partial AE onset dates will be imputed as follows:

If the onset date of an adverse event is missing day only, it will be set to:

- First day of the month that the AE occurred, if month/year of the onset of AE is different than the month/year of the study intervention start.
- The day of study intervention start, if the month/year of the onset of AE is the same as month/year of the study intervention start and month/year of the AE resolution date is different.
- The day of study intervention start or day of AE resolution date, whichever is earliest, if month/year of the onset of AE and month/year of the study intervention start date and month/year of the AE resolution date are same.

If the onset date of an adverse event is missing both day and month, it will be set to the earliest of:

- January 1 of the year of onset, as long as this date is on or after the study intervention start date.
- Month and day of the study intervention start date, if this date is the same year that the AE occurred.
- Last day of the year if the year of the AE onset is prior to the year of the study intervention start date.

Completely missing onset dates will not be imputed.

- Partial AE resolution dates not marked as ongoing will be imputed as follows:
 - If the resolution date of an adverse event is missing day only, it will be set to the earliest of the last day of the month of occurrence of resolution or the day of the date of death, if the death occurred in that month.
 - If the resolution date of an adverse event is missing both day and month, it will be set to the earliest of December 31 of the year or the day and month of the date of death, if the death occurred in that year.

Completely missing resolution dates will not be imputed.

- AE onset/resolution dates with missing times will be imputed as follows:
 - A missing time of onset of an adverse event will be set to the earlier of:
 - \circ 00:01 as long as the onset date is after the study intervention start date
 - The time of the study intervention start if this is the same day the AE occurred.
- The missing time of resolution of an adverse event will be set to 23:59.

If a missing time is associated with a partial or missing date, the date will be imputed first prior to imputing the time.

6.12. Appendix 12 CDAI

6.12.1. Partial CDAI Score Calculation Logic

• Pre-Calculation Logic

Step 1: Determine if a Partial CDAI total score can be calculated.

Sufficient CDAI Daily Diary data/components. CDAI score components are defined as:

- CDAI Daily Diary (participant diary) components:
 - 1. Number of liquid or soft stools each day for seven days
 - 2. Abdominal pain each day for seven days
 - 3. General well-being each day for seven days
 - 4. Fever (Yes/No)
 - 5. Anti-diarrhea medication (Yes/No)

For CDAI Daily Diary components, if there is not enough data in the previous 7 days (a minimum of 4 days of eligible diary data), then Partial CDAI total score cannot be calculated.

6.12.2. CDAI Score Calculation Logic

• **Pre-Calculation Logic**

Step 1: Determine if a CDAI total score can be calculated.

Sufficient CDAI Daily Diary data/components AND CDAI Site Form completion for the current visit is required to calculate a total CDAI Score. CDAI score components are defined as:

- CDAI Daily Diary (participant diary) components:
 - 6. Number of liquid or soft stools each day for seven days
 - 7. Abdominal pain each day for seven days
 - 8. General well-being each day for seven days
 - 9. Fever (Yes/No)
 - 10. Anti-diarrhea medication (Yes/No)
- CDAI Site Form (site worksheet) components:
 - 1. Manifestations (arthritis/arthralgia, iritis/uveitis, erythema nodosum/pyoderma gangrenosum/aphthous stomatitis, anal fissure, fistula or abscess and other fistula)
 - 2. Abdominal mass evaluation
 - 3. Hematocrit
 - 4. Weight

For CDAI Daily Diary components, if there is not enough data in the previous 7 days (a minimum of 4 days of eligible diary data), then CDAI total score cannot be calculated. For CDAI Site Form components, if the CDAI Site Form has not been completed (and synced) on the tablet for the current visit, then CDAI score cannot be calculated.

Step 2: Determine if there is missing data for the CDAI Evening Diary components:

- For the current visit's CDAI Site Form, if the site user enters bowel preparation and video ileocolonoscopy dates (required if they answered, 'Yes' to "Has the participant had a video ileocolonoscopy since their last site visit?") (CDAI Site Form questions ebf0226f-b3a0-433a-82a7-aefd0e510c93_Question and 422e412e-1189-4b32-bcef-b7481d90dec9_Question), then any diary entries (if in the previous 7 days) between and including those 2 dates entered should be ineligible for the current calculation.
- A minimum of 4 days of diary data entry is required for components from the participant's CDAI Evening Diary in the 7 days prior to the current visit activation date.

6.12.3. CDAI Score Calculation

Has the participant had a video ileocolonoscopy since the last site visit? Yes/no If yes,

[figure not shown]
Date of video ileocolonoscopy: _____

Date of the start of the bowel preparation: —

DISEASE ACTIVITY INDEX	SUM XFACTOR SUBTOTAL	
Total number of liquid or very soft stools in the previous 7 days	 	
Sum abdominal pain/cramps ratings		
(total for previous 7 days):	x 5 =	
0 = none $2 =$ moderate		
1 = mild $3 = severe$		
	_	
Sum general well-being ratings (total for previous 7 days):	x 7 =	
0 = generally well $3 = $ very poor		
1 = slightly under par $4 = $ terrible		
2 = poor		
Categories currently present and		
presumed to be related to Crohn's disease : $0 = no; 1 = yes$	•	
$\Box =$ arthritis/arthralgia	x 20 =	
$\Box = iritis/uveitis$	x 20 =	
$\Box =$ erythema nodosum/pyoderma gangrenosum/aphthous		
stomatitis	x 20 =	
$\Box =$ anal fissure, fistula or abscess	x 20 =	
$\Box =$ other fistula	x 20 =	
$\Box = $ fever over 100° F (37.8° C) during the previous 7		
days.	x 20 =	
During the previous 7 days has subject received antidiarrheal or		
opiate medications for diarrhea at least once:		
	x 30 =	
0 = no		
1 = yes		
Abdominal mass:	x 10 =	
0 = none $2 = $ questionable $5 = $ definite		
Hematocrit:	x 6 =	
Males: $(47-Hct) = SUM$	(add or subtract by sign)	
Females: $(42-Hct) = SUM$		
	*	
(Standard Weight - Actual Body Weight) x 100 =	x 1 =	
Standard Weight	(add or subtract by sign, round to 3 decimal places	s)
·o	, , , , , , , , , , , , , , , , , , ,	'
* If this value is less than -10 then enter -10 here.		
Standard weight and actual weight must be in same units (kg or	r lb)	
	TOTAL =	

(round total to integer)

6.13. Appendix 13: Liver Safety: Suggested Actions and Follow-up Assessments

ALL STUDIES SHOULD BE REPORTED WITH APPROPRIATE SOURCE DOCUMENTATION.

- > THE STUDY MEDICAL MONITOR SHOULD BE NOTIFIED WHEN THE ABNORMALITIES ARE DETECTED AND PROVIDED WITH AN UPDATE OF THE CONTINUED MONITORING RESULTS OF THE DIAGNOSTIC WORK-UP.
- CONSULT MEDICAL MONITOR FOR ANY QUESTIONS ON WORK -UP RECOMMENDATIONS, INCLUDING WHEN OPTIONAL TEST MAY BE INDICATED.
- A HEPATOLOGIST CONSULTATION SHOULD BE CONSIDERED IF CLINICALLY INDICATED FOR THE DIAGNOSIS AND MANAGEMENT OF POTENTIAL DILI.

Steps 1-6 should be performed for liver work-up when meeting the liver test algorithm (ie, $ALT \ge 3 \times ULN$) in which DILI is a possibility.

- 1. Obtain detailed history of present illness (abnormal LTs) including (if not already obtained at baseline) height, weight, body mass index. Assess for abdominal pain, nausea, vomiting, scleral icterus, jaundice, dark urine, pruritus, rash, fever, and lymphadenopathy. Assess for history of prior abnormal liver tests, liver disease including viral hepatitis, obesity, metabolic syndrome, congestive heart failure, occupational exposure to hepatotoxins, diabetes mellitus, gallstone disease or family history of gallstone or liver disease. Specifically record history of alcohol use, other medications including acetaminophen, nonsteroidal anti-inflammatory drugs, over-the-counter herbal supplements, vitamins, nutritional supplements, traditional Chinese medicines, and street drugs; and document whether or not there has been any recent change in any other prescription drugs and start-stop dates. Obtain travel history to endemic areas for hepatitis A, hepatitis E. Ask for history of any prior blood transfusions and when they were performed. Perform physical exam, obtain vital signs and body mass index, and document presence or absence of scleral icterus, palpable liver including size, degree of firmness or tenderness, palpable spleen including size, ascites, and stigmata of chronic liver disease (spider angiomata, gynecomastia, palmar erythema, testicular atrophy).
- 2. Imaging is strongly recommended to exclude other liver injury causes, particularly if TBili or ALP is >2 x ULN, or when clinically indicated based on medical history (eg, to exclude non-alcoholic hepatic steatosis). Imaging is mandatory if subject meets criteria for study intervention discontinuation according to the liver tests algorithm. Liver ultrasound is the recommended initial imaging modality with consideration of further imaging (eg, CT, MRI, magnetic resonance cholangiopancreatography, endoscopic retrograde cholangiopancreatography, Doppler studies of hepatic vessels, etc., if indicated based on ultrasound findings or clinical situation).
- 3. If TBili is ≥2 x ULN, request fractionation to document the fraction that is direct bilirubin and to rule out indirect hyperbilirubinemia indicative of Gilbert's syndrome, hemolysis or other causes of indirect hyperbilirubinemia.
- 4. Complete blood count with WBC, eosinophil, and platelet count (to further scrutinize potential immune-mediated mechanism of injury)

- 5. INR, and total protein and albumin (compute globulin fraction) should also be documented (to further scrutinize potential severity of the liver damage). If INR is abnormal, prothrombin time, partial thromboplastin time should be obtained and these values should be followed until normal, along with documentation of whether parenteral vitamin K was given along with the effect of such treatment on INR.
- 6. If initial LTs and ultrasound do not suggest Gilbert's syndrome, biliary tract disease or obstruction, viral hepatitis serology should be obtained including anti-hepatitis A virus immunoglobin (Ig)M, anti-hepatitis A virus total, HBsAg, anti-HBs, anti-HBc total, anti-HBc IgM, anti-HCV, anti-hepatitis E virus IgM (even if has not traveled to an endemic area for hepatitis E), Epstein-Barr virus, and cytomegalovirus screen.
 - If participant is immunosuppressed, test for HCV RNA and hepatitis E virus RNA by polymerase chain reaction.
 - If HBsAg or anti-HBc IgM or anti-HBc IgG positive, also get HBV DNA to detect active Hepatitis B, especially in patients who are immunosuppressed.
 - If all other hepatitis B serologic tests are negative and anti-HBc total is the only positive test, HBV DNA should be obtained to detect reactivation of hepatitis B.

Steps 7-12 are optional; In consultation with the Medical Monitor, additional clinical and laboratory studies may be performed to evaluate the underlying etiology of abnormal findings.

- 7. Based on potential baseline confounders of the disease target population consider (optionally): gamma-glutamyl transferase (to confirm the liver origin of elevated ALP levels), serum creatine phosphokinase (to confirm the liver origin of elevated AST levels], lactate dehydrogenase (to help exclude hemolysis), glutamate dehydrogenase (if muscle injury is suspected or if muscle disease is target population).
- 8. Assuming that the history, physical, and initial imaging and laboratory has not revealed a cause of elevated LTs, screen for other causes of liver disease including antinuclear antibody, anti-liver kidney microsomal antibody type 1, anti-liver-kidney microsomal antibodies, anti-smooth muscle antibodies (to screen for additional immune-related etiologies), erythrocyte sedimentation rate, and CRP (to screen for potential systemic inflammatory causes).
- 9. If the pattern of laboratory abnormalities is not hepatocellular, but cholestatic or a mixed pattern (see definitions below), then gamma-glutamyl transferase, anti-mitochondrial antibody (AMA) and anti-neutrophil cytoplasmic antibody should also be tested. If there is an indication by history or elevated baseline LTs that there may be an underlying chronic liver disease possibly exacerbated by exposure to the study intervention in the clinical trial or making the participant more susceptible to DILI, test iron/total iron binding capacity and ferritin (hemochromatosis), and alpha-1-antitrypsin level. If patient is <50 years of age, ceruloplasmin should also be tested to screen for Wilson's disease. If patient is sick enough to be hospitalized and is under age 50, a slit lamp examination to detect Kayser-Fleischer rings and a 24-hour urine collection for copper should be measured. Consider serum ethanol and/or acetaminophen level and urine drug screen as clinically appropriate.

Patterns of DILI Based on Elevations of Liver Tests

Histopathology	LT	Ratio (ALT/ULN) / (ALP/ULN)
Hepatocellular	ALT ≥3 × ULN	≥5
Cholestatic	ALT ≥3 × ULN	≤2
Mixed	ALT \geq 3 × ULN and AP \geq 2 × ULN	>2 to <5

10. A liver biopsy should be considered if autoimmune hepatitis remains a competing etiology and if immunosuppressive therapy is contemplated.

A liver biopsy may be considered:

- if there is unrelenting rise in liver biochemistries or signs of worsening liver function despite stopping the suspected offending agent.
- if peak ALT level has not fallen by >50% at 30-60 days after onset in cases of hepatocellular DILI, or if peak ALP has not fallen by >50% at 180 days in cases of cholestatic DILI despite stopping the suspected offending agent.
- in cases of DILI where continued use or re-exposure to the implicated agent is expected.
- if liver biochemistry abnormalities persist beyond 180 days to evaluate for the presence of chronic liver diseases and chronic DILI.
- 11. If pertinent, copies of hospital discharge summary, radiology, pathology and autopsy reports should be obtained.
